### 11.1 Response Considerations

Schedule of Evaluations: PET/CT or whole body CT scans are required at baseline for all patients. For the purposes of this study, patients should be reevaluated for disease progression at the end of each cycle. In addition to a baseline PET/CT scan, confirmatory scans should also be obtained at Day 1 of Cycles 4, 8, 12 and 18 (Section 4). During observation, CT scan should be obtained every 3 months during the first year to evaluate for disease progression.

Definitions for clinical response for patients with lymphoma are from the recently revised Cheson's et al criteria published in 2014 (Cheson, Fisher et al. 2014), derived from the original criteria published in 2007 (Cheson 2007). Lymph node measurements should be taken from the CT portion of the PET/CT, or other dedicated CT scans where applicable. Measurement of lymphadenopathy for purposes of assessing for PR will be determined by adding the sum of the products of the maximal perpendicular diameters of measured lesions (SPD). The PPD of a single node is sufficient to evaluate for PD (see Table 11.2). Measurable extranodal disease should be assessed in a manner similar to that for nodal disease. For these recommendations, the spleen is considered nodal disease. Disease that is only assessable (eg, pleural effusions, bone lesions) will be recorded as present or absent only, unless, while an abnormality is still noted by imaging studies or physical examination, it is found to be histologically and pathologically negative.

Response is based on PET/CT based on the revised 2014 Lugano Classification (Cheson, Fisher et al. 2014).

### 11.2 Lugano Classification Response criteria (Cheson, Fisher et al. 2014)

	PET-CT Based Response	CT-Based Response
Complete Response	Complete metabolic response (CMR)	Complete radiologic response (CR) (all of the following)
Lymph nodes and extralymphatic sites	Score 1, 2, or 3* with or without a residual mass on SPS† It is recognized that in Waldeyer's ring or extranodal sites with high physiologic uptake or with activation	Target nodes/nodal masses must regress to $\leq 1.5$ cm in LDi No extralymphatic sites of disease

	PET-CT Based Response	CT-Based Response
	within spleen or marrow (eg, with chemotherapy or myeloid colony-stimulating factors), uptake may be greater than normal mediastinum and/or liver. In this circumstance, complete metabolic response may be inferred if uptake at sites of initial involvement is no greater than surrounding normal tissue even if the tissue has high physiologic uptake	
Nonmeasured lesion	Not applicable	Absent
Organ enlargement	Not applicable	Regress to normal
New lesions	None	None
Bone marrow	No evidence of FDG-avid disease in marrow	Normal by morphology; if indeterminate, IHC negative
Partial Response	Partial metabolic response (PMR)	Partial remission (PR) (all of the following)
Lymph nodes and extralymphatic sites	Score 4 or 5† with reduced uptake compared with baseline and residual mass(es) of any size At interim, these findings suggest responding disease At end of treatment, these findings indicate residual disease	≥50% decrease in SPD of up to 6 target measurable nodes and extranodal sites When a lesion is too small to measure on CT, assign 0.5 cm X 0.5 cm as the default value When no longer visible, 0.0 X 0.0 cm For a node >0.5 cm X 0.5 cm, but smaller than normal, use actual measurement for calculation
Nonmeasured lesions	Not applicable	Absent/normal, regressed, but no increase
Organ enlargement	Not applicable	Spleen must have regressed by >50% in length beyond normal
New lesions	None	None
Bone marrow	Residual uptake higher than uptake in normal marrow but reduced compared with baseline (diffuse uptake compatible with reactive changes from chemotherapy allowed). If there are persistent focal changes in the marrow in the context of a nodal response, consideration should be given to further evaluation with MRI or biopsy or an interval scan	Not Applicable
No Response or Stable Disease	No metabolic response (NMR)	Stable disease (SD)
Target nodes/nodal masses, extranodal lesions	Score 4 or 5 with no significant change in FDG uptake from baseline at interim or end of treatment	<50% decrease from baseline in SPD of up to 6 dominant, measurable nodes and extranodal sites; no criteria for progressive disease are met
Nonmeasured	Not applicable	No increase consistent with

	PET-CT Based Response	CT-Based Response
lesions		progression
Organ enlargement	Not applicable	No increase consistent with progression
New lesions	None	None
Bone marrow	No change from baseline	Not Applicable
Progressive disease	Progressive metabolic disease (PMD)	Progressive disease (PD) requires at least 1 of the following
Individual target nodes/nodal masses	Score 4 or 5 with an increase in intensity of uptake from baseline and/or	PPD progression:  An individual node/lesion must be abnormal with: LDi >1.5 cm and Increase by $\geq 50\%$ from PPD nadir and An increase in LDi or SDi from nadir 0.5 cm for lesions $\leq 2$ cm 1.0 cm for lesions $> 2$ cm In the setting of splenomegaly, the splenic length must increase by $> 50\%$ of the extent of its prior increase beyond baseline (eg, a 15-cm spleen must increase to $> 16$ cm). If no prior splenomegaly, must increase by at least 2 cm from baseline New or recurrent splenomegaly
Extranodal lesions	New FDG-avid foci consistent with lymphoma at interim or end-of-treatment assessment	
Nonmeasured lesions	None	New or clear progression of preexisting nonmeasured lesions
New lesions	New FDG-avid foci consistent with lymphoma rather than another etiology (eg, infection, inflammation). If uncertain regarding etiology of new lesions, biopsy or interval scan may be considered	Regrowth of previously resolved lesions A new node $> 1.5$ cm in any axis A new extranodal site $> 1.0$ cm in any axis; if $< 1.0$ cm in any axis, its presence must be unequivocal and must be attributable to lymphoma Assessable disease of any size unequivocally attributable to lymphoma
Bone marrow	New or recurrent FDG-avid foci	New or recurrent involvement
Abbreviations: 5PS, 5-point scale; CT, computed tomography; FDG, fluorodeoxyglucose; IHC, immunohistochemistry; LDi, longest transverse diameter of a lesion; MRI, magnetic resonance imaging; PET, positron emission tomography; PPD, cross product of the LDi and perpendicular diameter; SDi, shortest axis perpendicular to the LDi; SPD, sum of the product of the perpendicular diameters for		

	PET-CT Based Response	CT-Based Response
multiple lesions.	
*A score of 3 in many patients indicates a good prognosis with standard treatment, especially if at the time of an interim scan. However, in trials involving PET where de-escalation is investigated, it may be preferable to consider a score of 3 as inadequate response (to avoid undertreatment). Measured dominant lesions: Up to six of the largest dominant nodes, nodal masses, and extranodal lesions selected to be clearly measurable in two diameters. Nodes should preferably be from disparate regions of the body and should include, where applicable, mediastinal and retroperitoneal areas. Non-nodal lesions include those in solid organs (eg, liver, spleen, kidneys, lungs), GI involvement, cutaneous lesions, or those noted on palpation. Nonmeasured lesions: Any disease not selected as measured, dominant disease and truly assessable disease should be considered not measured. These sites include any nodes, nodal masses, and extranodal sites not selected as dominant or measurable or that do not meet the requirements for measurability but are still considered abnormal, as well as truly assessable disease, which is any site of suspected disease that would be difficult to follow quantitatively with measurement, including pleural effusions, ascites, bone lesions, leptomeningeal disease, abdominal masses, and other lesions that cannot be confirmed and followed by imaging. In Waldeyer's ring or in extranodal sites (eg, GI tract, liver, bone marrow), FDG uptake may be greater than in the mediastinum with complete metabolic response, but should be no higher than surrounding normal physiologic uptake (eg, with marrow activation as a result of chemotherapy or myeloid growth factors).
 
†PET Deauville 5PS: 1, no uptake above background; 2, uptake <math>\leq</math> mediastinum; 3, uptake <math>></math> mediastinum but <math>\leq</math> liver; 4, uptake moderately <math>></math> liver; 5, uptake markedly higher than liver and/or new lesions; X, new areas of uptake unlikely to be related to lymphoma.
	

Note: Transformation to a more aggressive histology that requires a change in active treatment will be considered progressive disease.

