### 3.0 Patient Eligibility

#### 3.1 Inclusion Criteria

- 3.11 Age  $\geq 18$  years.
- 3.12 Histological confirmation of biopsy-proven non-Hodgkin lymphoma, *excluding* chronic lymphocytic leukemia, primary CNS lymphoma and Burkitt's lymphoma.  
Note: Small lymphocytic lymphoma (SLL) is allowed.
- 3.13 Patients with indolent NHL must have had  $\geq 1$  regimen of rituximab-containing regimen.  
Note: This includes FL, marginal lymphoma and MALT.
- 3.14 Patients with aggressive NHL must have had  $\geq 2$  regimens.  
Note: This includes DLBCL, MCL, PMBCL, and T cell lymphoma.
- Patients with aggressive NHL must have received prior therapy – at a minimum:
- Anti-CD20 monoclonal antibody unless tumor is CD20 negative and
  - An anthracycline containing regimen.
  - Transformed FL must have had therapy for FL and be refractory to chemotherapy for DLBCL.
- Chemotherapy refractory disease in aggressive NHL is defined as
- Stable disease of  $\leq 12$  months or progressive disease as best response to most recent chemotherapy containing regimen.
  - Disease progression or recurrence  $\leq 12$  months of prior autologous SCT.
- Patients with aggressive NHL must have failed autologous HSCT, or are ineligible or not consenting to autologous HSCT.
- 3.15 Patient must have at least 3 measurable lesions that are  $\geq 1.5$  cm in one dimension. One of the lesions must be  $\geq 2.0$  cm and is amenable to image-guided cryoablation and multiple vaccine injections as determined by Interventional Radiology and PI (including tumors that can be safely accessed using imaging guidance and treated with minimal risk to adjacent structures).
- 3.16 ECOG Performance Status (PS) 0 or 1 (Appendix I).
- 3.17 The following laboratory values obtained  $\leq 14$  days prior to registration.
- Absolute neutrophil count (ANC)  $\geq 1000/\text{mm}^3$
  - Absolute lymphocyte count  $\geq 200/\text{mm}^3$
  - Platelet count  $\geq 50,000/\text{mm}^3$
  - Hemoglobin  $\geq 8.0$  g/dL
  - Total bilirubin  $\leq 1.5$  x upper limit of normal (ULN), unless due to Gilbert's disease.
  - Aspartate transaminase (AST/SGOT) and alanine transaminase (ALT/SGPT)  $\leq 2.5$  x ULN
  - Creatinine  $\leq 1.5$  x ULN or calculated creatinine clearance  $\geq 60$  mL/min for subject with creatinine  $> 1.5$  x institutional ULN
- 3.18 Negative serum pregnancy test for women of childbearing potential  $\leq 7$  days prior to registration.  

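### PET-CT complete response requires no baseline FDG avidity, so an unchanged non-avid patient is a complete response in table 11.2 but stable disease under 11.21–11.23, and the plan does not say which prevails

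*Combined protocol and SAP*

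**What the plan says.** **Entry.** Section 3.15 opens "Patient must have at least 3 measurable lesions that are" 1.5 cm or larger in one dimension, and adds that one must be at least 2.0 cm and suitable for cryoablation. Neither 3.1 nor 3.2 mentions FDG uptake. On histology, 3.12 notes "Small lymphocytic lymphoma (SLL) is allowed", and the note to 3.13 on indolent disease reads "Note: This includes FL, marginal lymphoma and MALT".

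**Imaging.** Section 11.1 states "PET/CT or whole body CT scans are required at baseline for all patients", so a baseline PET is not assured. The same section states "Response is based on PET/CT based on the revised 2014 Lugano Classification". No sentence sends non-avid disease to the CT column.

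**Table 11.2, PET-CT column.** Complete metabolic response is "Score 1, 2, or 3* with or without a residual mass on SPS", with no new lesions and no avid marrow disease. The partial response row needs a score of 4 or 5 with reduced uptake. The no-response row is "Score 4 or 5 with no significant change in FDG uptake from baseline at interim or end of treatment". Progression needs a score of 4 or 5 with rising uptake, or new avid foci.

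**Sections 11.21 and 11.23.** Complete response requires every listed condition. These include disappearance of detectable clinical disease (11.211) and, on CT, shrinkage to 1.5 cm or less of nodes that were larger before therapy (11.212). A patient who reaches neither complete nor partial response and has not progressed is stable (11.231), and 11.232 describes stable disease as unchanged lesion size on CT.

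**Endpoint.** Success is a partial or complete response (16.11, 16.3211). The regimen is called promising with 13 or more responders among 28 (16.312). Section 16.314 gives 81% power at a one-sided error of 0.05, for 30% against 53%.

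**The concern.** The complete response row of the PET-CT column is an absolute score. It asks neither for a score of 4 or 5 at baseline nor for any change. Because the partial response and no-response rows both need a score of 4 or 5, unchanged disease that scores 1 to 3, without new or marrow foci, has only one place to go in that column: complete response. There is no stable category for it.

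Two kinds of patient are affected. The first has a baseline PET/CT that already scores 1 to 3. The second has CT only at baseline and a first PET on treatment that scores 1 to 3; nothing then shows whether uptake fell or was never raised. A confirmatory scan does not help, because a lesion that was never avid will normally score low again.

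At stake is success or failure in the primary endpoint, in a single-arm trial with no control group to expose the error. The same label also feeds the complete-response provisions of 7.113 and 7.15, so those sections inherit the ambiguity.

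**Working it through.** **1. The same patient under each text.** Assume a non-cryoablated node above 1.5 cm, score 1 to 3 at baseline and at Cycle 4, same size, no new lesions, marrow clear.

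| Text | Condition | Result |
|---|---|---|
| 11.2, PET-CT column | score 1 to 3; a remaining mass is allowed | complete response |
| 11.2, CT column | target nodes must reach 1.5 cm or less | not complete response |
| 11.211–11.212 | disease gone, nodes shrunk on CT | not complete response |
| 11.221 | at least a 50% fall in the sum of products | not partial response |
| 11.23 | neither complete nor partial response, no progression, no size change | stable disease |

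So the patient is a success by one text and a failure by another. Section 11.1 points to PET/CT; 11.21 says all of its conditions are needed. Section 11.227 calls for CT criteria, but only for partial response. Section 16.41 refers overall response to CT or PET/CT under Section 11, so it does not settle the matter.

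**2. The plan's own figures.** Inputs: n = 28, cut-off 13, null 30%, alternative 53% (16.31, 16.312, 16.314). Exact binomial:

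- Error: P(X ≥ 13 | 28, 0.30) = 0.0491
- Power: P(X ≥ 13 | 28, 0.53) = 0.8122

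Both agree with the stated 0.05 ceiling and 81%. A cut-off of 12 would give an error of 0.1028, so 13 is the smallest cut-off that respects the ceiling.

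**3. If the PET-CT column governs.** Let k of the 28 be automatic responders and let the other 28 − k respond at the null rate of 30%. The rule is then met with probability P(Bin(28 − k, 0.30) ≥ 13 − k). The expected observed response rate is [k + 0.30(28 − k)]/28.

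| k (assumed) | Share of 28 | Tail | Expected observed rate | One-sided error |
|---|---|---|---|---|
| 0 | 0% | Bin(28) ≥ 13 | 8.4/28 = 30.0% | 0.049 |
| 1 | 3.6% | Bin(27) ≥ 12 | 9.1/28 = 32.5% | 0.080 |
| 2 | 7.1% | Bin(26) ≥ 11 | 9.8/28 = 35.0% | 0.125 |
| 3 | 10.7% | Bin(25) ≥ 10 | 10.5/28 = 37.5% | 0.189 |

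The number affected can instead be treated as random, with each patient affected with probability f. The response probability is then f + 0.30(1 − f). For f = 5, 10, 15 and 20% this is 33.5, 37.0, 40.5 and 44.0%, and the error is 0.107, 0.200, 0.324 and 0.470. These values of f are also assumptions.

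**4. If 11.21 governs.** Unchanged nodes above 1.5 cm are not complete responses. Then k = 0, and error and power stay at 0.049 and 0.812.

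**The case against.** The strongest reply is that Section 11 already contains the safeguard. Sections 11.211 and 11.212 are conjunctive conditions for complete response, and 11.23 places unchanged lesions in stable disease. CT is also a recognised route: it is accepted at baseline, node sizes are taken from it, table 11.2 has a full CT column, and no sentence orders a patient with a CT baseline to be switched to PET. Section 11 adopts a cited 2014 classification, which may itself limit the PET-CT column to avid disease; that cannot be checked from these documents. The frequency of non-avid disease is not given, and entry also admits DLBCL, MCL, PMBCL, T-cell lymphoma and FL. Finally, stopping after a complete response under 7.113 and 7.15 is discretionary, not automatic.

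Much of this stands. It rules out two stronger readings that a reader might infer: that an unchanged non-avid patient simply is a complete response under this protocol, and that the 13-of-28 rule has lost its 5% error. Neither follows while 11.21 and 11.23 remain in force.

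The reply does not close the gap. If 11.212 always applies, the PET-CT row's allowance for a remaining mass has no effect for a node left above 1.5 cm, in avid patients as well. An assessor who follows 11.1 and uses the PET-CT column has therefore already set 11.212 aside. The two texts cannot both govern, and nothing ranks them.

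**Conclusion.** The point holds as an unreconciled definition of complete response. Table 11.2 and Sections 11.21–11.23 classify the same unchanged, non-avid patient in opposite ways on the primary endpoint, and the column to which 11.1 points is the one that counts a success without any change in disease.

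The effect on the decision rule is conditional. It needs the PET-CT column to prevail and at least one such patient among the 28. On those terms a single patient takes the error from 0.049 to 0.080, and three take it to 0.189, with all others assumed to respond at 30%. If 11.21 prevails there is no inflation. The counts are a sensitivity range, not an estimate. The correction is worth making because it bears on the primary endpoint and costs almost nothing.

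**What to change.** In Section 11.1, state three things:

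- The PET-CT column of table 11.2 is used for response only in patients whose baseline PET/CT shows a score of 4 or 5 in at least one non-cryoablated lesion.
- All other patients, including those without a baseline PET/CT, are classified by the CT column. All-cutaneous target disease stays under 11.31.
- When a mass remains, either table 11.2 or Sections 11.21–11.23 governs complete response, and the other text is amended to agree.

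The third statement is needed as well as the first two. Without it, an avid patient who falls to a score of 1 to 3 with a node still above 1.5 cm remains a complete response in the table and not one under 11.212. All three should be settled before the final response classification and applied to every patient in the analysis, including those carried over from phase I.

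The cost is a few sentences. No extra scans are needed, because 11.1 already takes node measurements from CT or from the CT part of the PET/CT. The downside is that the observed response rate may be lower.

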#### 11.21 Complete Response (CR).

The designation of CR requires all of the following:

- 11.211 Complete disappearance of all detectable clinical evidence of disease and definitely disease-related symptoms if present before therapy.
- 11.212 All lymph nodes and nodal masses must have regressed on CT to normal size ( $\leq 1.5$  cm in their greatest transverse diameter for nodes  $> 1.5$  cm before therapy). Previously involved nodes that were 1.1 to 1.5 cm in their long axis and more than 1.0 cm in their short axis before treatment must have decreased to  $\leq 1.0$  cm in their short axis after treatment.
- 11.213 The spleen and/or liver, if considered enlarged before therapy on the basis of a physical examination or CT scan, should not be palpable on physical examination and should be considered normal size by imaging studies, and nodules related to lymphoma should disappear. However, determination of splenic involvement is not always reliable because a spleen considered normal in size may still contain lymphoma, whereas an enlarged spleen may reflect variations in anatomy, blood volume, the use of hematopoietic growth factors, or causes other than lymphoma. Similarly, other organs considered to be enlarged before therapy due to involvement by lymphoma, such as liver and kidneys, must have decreased in size.

11.214 If the bone marrow was involved by lymphoma before treatment, the infiltrate must have cleared on repeat bone marrow biopsy. The biopsy sample on which this determination is made must be adequate (with a goal of >20 mm unilateral core). If the sample is indeterminate by morphology, it should be negative by immunohistochemistry. A sample that is negative by immunohistochemistry but that demonstrates a small population of clonal lymphocytes by flow cytometry will be considered a CR until data become available demonstrating a clear difference in patient outcome.

#### 11.22 Criteria for Partial Response (PR)

The designation of PR requires all of the following:

11.221 At least a 50% decrease in sum of the product of the diameters (SPD) of up to six of the largest dominant nodes or nodal masses. These nodes or masses should be selected according to all of the following:

- they should be clearly measurable in at least 2 perpendicular dimensions
- if possible they should be from disparate regions of the body
- they should include mediastinal and retroperitoneal areas of disease whenever these sites are involved

11.222 No increase should be observed in the size of other nodes, liver, or spleen.

11.223 Splenic and hepatic nodules must regress by  $\geq 50\%$  in their SPD or, for single nodules, in the greatest transverse diameter.

11.224 With the exception of splenic and hepatic nodules, involvement of other organs is usually assessable and no measurable disease should be present.

11.225 Bone marrow assessment is irrelevant for determination of a PR if the sample was positive before treatment. However, if positive, the cell type should be specified (eg, large-cell lymphoma or small neoplastic B cells). Patients who achieve a CR by the above criteria, but who have persistent morphologic bone marrow involvement will be considered partial responders.

When the bone marrow was involved before therapy and a clinical CR was achieved, but with no bone marrow assessment after treatment, patients should be considered partial responders.

11.226 No new sites of disease should be observed.

11.227 CT criteria should be used.

#### 11.23 Criteria for Stable Disease (STAB)

11.231 A patient is considered to have SD when he or she fails to attain the criteria needed for a CR or PR (see above), but does not fulfill those for progressive disease (see below).

11.232 There must be no change in the size of the previous lesions on the post-treatment CT scan.

#### 11.24 Relapsed Disease (after CR)/Progressive Disease (after PR, SD)

Lymph nodes should be considered abnormal if the long axis is more than 1.5 cm regardless of the short axis. If a lymph node has a long axis of 1.1 to 1.5 cm, it should only be considered abnormal if its short axis is more than 1.0. Lymph nodes  $\leq 1.0 \times \leq 1.0$  cm will not be considered as abnormal for relapse or progressive disease.

- 11.241 Appearance of any new lesion more than 1.5 cm in any axis during or at the end of therapy, even if other lesions are decreasing in size. Increased FDG uptake in a previously unaffected site should only be considered relapsed or progressive disease after confirmation with other modalities. In patients with no prior history of pulmonary lymphoma, new lung nodules identified by CT are mostly benign. Thus, a therapeutic decision should not be made solely on the basis of the PET without histologic confirmation.
- 11.242 At least a 50% increase from nadir in the SPD of any previously involved nodes, or in a single involved node, or the size of other lesions (eg, splenic or hepatic nodules). To be considered progressive disease, a lymph node with a diameter of the short axis of less than 1.0 cm must increase by 50% and to a size of 1.5 x 1.5 cm or more than 1.5 cm in the long axis.
- 11.243 At least a 50% increase in the longest diameter of any single previously identified node more than 1 cm in its short axis.
- 11.244 Transformation to a more aggressive histology that requires a change in active treatment will be considered progressive disease.

